Hypothesis: Treatment with glargine U300 will result in equivalent glycemic control in hospitalized patients with T2D. Glargine U300 will result in lower number of hypoglycemia compared to glargine.

Aim 2: To determine differences in glycemic control after hospital discharge between treatment with glargine U300 and glargine U100 in medicine and surgery patients T2D. Patients with poorly controlled diabetes ($HbA1c \geq 7.5\%$) enrolled in Aim 1 will be invited to participate in this open label prospective outpatient study. The total duration of the study is 3 months. Patients with an $HbA1c$ between 7.5% and 10% will be discharged on preadmission oral antidiabetic agents plus glargine U300 and U100 once daily. Patients with an admission $A1C \geq 10\%$ will be discharged on basal bolus regimen with glargine and glulisine insulin before meals.

Hypothesis: treatment with glargine U300 and U100 will result in a similar improvement in HbA1c levels after hospital discharge. Glargine U300 will result in lower number of hypoglycemia compared to U100.

II. BACKGROUND AND CURRENT STATUS OF WORK IN THE FIELD.

Inpatient glycemic control in non-ICU setting. A large body of evidence has shown that in hospitalized patients, the presence of hyperglycemia and diabetes is associated with increased risk of complications and death (1-6, 28-31). Several randomized multi-center trials have shown that the use of basal bolus insulin regimen result in improved glycemic control and reduced rate of hospital complications compared to sliding scale regular insulin (SSI) in patients with T2D (12-14). We have reported that treatment with basal and basal bolus regimens using glargine U100 results in greater improvement in BG control and a reduction in the frequency of hospital complications including postoperative wound infection, pneumonia, bacteremia, and acute renal and respiratory failure compared to SSI treatment.(16, 17, 32, 33) In addition, the use of basal bolus regimen with glargine U100 is safe with low rate of hypoglycemic events. Based on these studies and others, clinical practice guidelines for the management of hyperglycemia in non-ICU setting have favored the use of basal prandial insulin regimens with insulin analogs for most inpatients with T2D (6, 19, 31).

Efficacy and safety of new glargine U-300 insulin:

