V. Aim 2: To determine differences in glycemic control after hospital discharge between treatment with glargine U300 and glargine U100 in medicine and surgery patients T2D.

[figure not shown]
V.a. Rationale. Few studies have addressed the efficacy of insulin alone or in combination with oral agents after hospital discharge. In a recent study (see preliminary results section), patients were discharged on a combination of OADs and glargine U100 insulin or on a basal bolus regimen according to bA1c levels and achieved a marked reduction in HbA1c from 8.75% on admission to 7.9% and 7.35% after 4 and 12 weeks of hospital discharge. However, the use of glargine U100 alone or in combination to oral agents or as basal bolus insulin resulted in 30% and close to 40% incidence of hypoglycemia, respectively. In this study, we will compare the efficacy and safety of glargine U300 and U100 after hospital discharge. The total duration of the study is 3 months. Several outpatient insulin trials have shown that treatment with glargine U300 results in similar improvement in glycemic control, but in significant reduction in hypoglycemia compared to glargine U100 (23-27). Thus we expect that glargine U300 will be a safer alternative to current use of glargine U100 formulation.

V.b Insulin Discharge algorithm:

Patients with poorly controlled diabetes ($HbA1c \geq 7.5\%$) enrolled in Aim 1 will be invited to participate in this open label prospective outpatient study. The total duration of the study is 3 months.

- Patients with admission Hba1c < 7.5% will be discharged on their preadmission antidiabetic regimen and will not be included in the Aim 2 outpatient study.
- Patients with no previous pharmacological treatment prior to admission will be discharged on 50% of daily basal insulin (glargine U300 or glargine U100) hospital dose.
- Patients on oral agents prior to admission with an HbA1c between 7.5% and <10% will be discharged on oral agents plus glargine U300 or glargine U100 at 50% of the daily hospital dose.
- Patients on oral agents prior to admission with an admission A1C ≥ 10% will be discharged on their oral agents plus glargine U300 or glargine U100 at 80% of daily hospital dose. If previous basal bolus only therapy or contraindications to previous oral therapy, discharge on basal bolus at 100% of daily hospital dose.

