GLP1-RA. GLP1-RA treatment is considered background medication (non-investigational medicinal product) and will not be provided during the trial. No dose adjustment or up-titration will occur during the trial.

SGLT2-i. The use of SGLT2-I is considered background medication (non-investigational medicinal product) and will not be provided during the trial. No dose adjustment or up-titration will occur during the trial.

V.c. Hospital Diabetes Education. Prior to discharge, participants will be trained in:

1. Diabetes education if not received within 1 year of admission
2. Recommended targets for fasting and premeal blood glucose between 90 to 130 mg/dL
3. Use of glucose meters for home glucose self-monitoring
4. Keeping BG records, and will receive a logbook to record glucose tests results.
5. Hypoglycemia prevention, recognition and management
6. Insulin administration

V.d. Follow-up Care:

- Provide glargine insulin 1-month supply at each clinic visit.
- A member of the diabetes research team will contact patients via telephone call every 2 weeks for a total of 3 months.
- Patients will be asked to attend outpatient visits at 1 and 3 month after hospital discharge.
- Recommendation on insulin adjustment to be provided after each telephone contact and/or clinic visit by a licensed physician (fellow or study physician) (section V.f).

V.e. During follow up we will collect the following information:

1. Glycemic control:
 - a. Mean daily fasting and premeal blood glucose levels
 - b. HbA1C at 1 and 3 months after hospital discharge
 - c. Hypoglycemic events (BG < 70 mg/dl and < 40 mg/dl)
 - d. Hyperglycemic events (BG > 240 mg/dl)
2. Diabetes treatment:
 - a. Insulin dosage (unit/day)
 - b. Use of oral agents

- c. Protocol adherence
- 3. Clinical Outcome:
 - a. Hospital readmissions
 - b. Emergency room visits
 - c. Postoperative complications

V.f. Primary care physicians will be provided with the following algorithm for outpatient basal insulin dose adjustment every 2 weeks:

Basal Insulin (glargine U300 and glargine U100)	
If mean FBG > 180 mg/dL for the last 3 consecutive days and no hypoglycemia or no random BG (RBG) <70 mg/dL	Increase daily dose by 4 IU
If mean FBG > 140 mg/dL for the last 3 consecutive days and no hypoglycemia < or no RBG <70 mg/dL	Increase daily dose by 2 IU
If mean FBG between 100 - 140 mg/dL and no hypoglycemia or no RBG <70 mg/dL	No Change
If any FBG between 70 – 99 mg/dl	Decrease by 4 IU or 10% of total daily dose

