If any FBG or RBG 40- 69 mg/dl	Decrease by 8 IU or 20% of total daily dose
If any FBG or RBG < 40 mg/dl	Decrease total daily dose by 30 - 40%

V.g. Aim 2. Statistical Analysis:

V.g.1. Sample Size and Power Calculations: The primary endpoint in Aim 2 is difference in glycemic control (mean daily BG) after hospital discharge. Under the same assumptions for equivalence margin and BG variability as in Aim 1, we have the same sample size requirement (i.e. 78 subjects per group after 10% attrition). Accounting for 10% attrition rate, we would need 90 patients per treatment group (total # of patients to be recruited: 180 subjects, 90 per treatment group), to achieve >80% power.

V.g.2. Analysis of Primary Endpoint:

The primary endpoint in this study is glycemic control measured by mean daily BG concentration after hospital discharge. Secondary outcomes include rate of hypoglycemia during follow-up, change in HbA1c, body weight in kilograms, number of episodes of severe hyperglycemia, complications and emergency room visits or hospital readmissions at 12 weeks post-discharge. To analyze these outcomes, we will follow the same analytic strategy proposed for the secondary endpoints of Aim 1. We will first compare the primary outcome using two-sample t-tests (or Wilcoxon tests) or one-way ANOVA, followed by multivariate linear regression to estimate and test the difference between the two treatment groups while simultaneously accounting for other potential confounders. Transformations will be applied if normality violation is detected. Stepwise, backward, or forward model selection strategy will be adopted to determine the variables to be included in the final model. Standard diagnostic and model checking procedures will be applied to examine the fit of the developed models.

DATA HANDLING AND RECORD KEEPING:

Data collection records with personal identifiers will be stored in locked file cabinets. Presentation of the study results at regional or scientific meetings or in publications will not identify subjects. Access to research and confidential records will be limited to clinical investigators, research coordinators, and the IRB at Emory University.

All data will be entered electronically in Redcap by participating sites. Sponsor site expects data to be entered in Redcap within 10 days of phone call or outpatient visit.

VI. Methods and Procedures Applied to Human Subjects:

VI.a. Subject Population:

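### Aim 2 names only a patient-kept logbook as the record of home glucose in an open-label study, so selective transcription could differ by arm; reading the meter at the two planned visits would remove that risk

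*Combined protocol and SAP*

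**What the plan says.** Section V.b describes Aim 2 as open label: patients with HbA1c of 7.5% or more "enrolled in Aim 1 will be invited to participate in this open label prospective outpatient study". Section V.g.2 sets the endpoint: "The primary endpoint in this study is glycemic control measured by mean daily BG concentration after hospital discharge". It continues: "Secondary outcomes include rate of hypoglycemia during follow-up, change in HbA1c, body weight in kilograms".

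Section V.e lists the follow-up data, including "Mean daily fasting and premeal blood glucose levels" and "Hypoglycemic events (BG < 70 mg/dl and < 40 mg/dl"). It does not say where these values come from.

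Home measurement appears in section V.c, the list of topics taught before discharge. Item 3 is "Use of glucose meters for home glucose self-monitoring" and item 4 is "Keeping BG records, and will receive a logbook to record glucose tests results". No other record of home glucose is named. Nothing provides for downloading the meter, reading its memory or checking the logbook against it, and no number of readings per day is set.

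Section V.d adds telephone calls every two weeks and clinic visits at 1 and 3 months. The Aim 2 flow chart marks hypoglycemia at all six contacts after discharge (weeks 2, 4, 6, 8, 10 and 12), and fasting BG at weeks 4 and 12 only. HbA1c is measured by blood sample at 1 and 3 months (V.e, VIII.a).

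The Aim 2 hypothesis under Specific Aims states a direction: "Glargine U300 will result in lower number of hypoglycemia compared to U100".

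**The concern.** A daily mean over three months cannot come from two clinic visits, so the primary endpoint must rest mainly on home readings. With a logbook, the patient decides which meter results are copied. Patients and staff know the arm, and the protocol itself expects fewer low values on U300. Patients are also taught a target range of 90 to 130 mg/dl (V.c, item 2), which gives a reason to leave out values outside it.

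Omission at the same rate in both arms would leave the BG difference largely intact and only lower the event counts. Omission at different rates would shift the BG difference that is to be judged against 18 mg/dl. It would also shift the hypoglycemia comparison, where U300 is expected to do better. Readings never transcribed cannot be recovered at the analysis stage unless the meter memory was kept.

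**Working it through.** **The plan's own figure.** V.g.1 carries over the Aim 1 assumptions: margin 18 mg/dl, SD 45 mg/dl, true difference 0, one-sided two-sample t-test, 80% power. Alpha is not stated. One-sided 0.05 gives 78 per group, as stated; one-sided 0.025 would give 99. The point concerns data capture and does not dispute these figures. The standard error with 78 per group is 45 × √(2/78) = 7.2 mg/dl.

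**Inputs that are assumptions.** The documents give no rate of recording error and no SD for single readings (45 mg/dl refers to mean daily BG). A reading SD of 40 to 60 mg/dl, normal readings and the omission rates below are assumed, to show scale only.

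**Mean BG.** Leaving out the highest fraction q of normal readings lowers their mean by SD × φ(z₁₋q)/(1−q).

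- q = 5%: 0.1031/0.95 = 0.1086 SD.
- q = 10%: 0.1755/0.90 = 0.1950 SD.
- Difference between an arm omitting 10% and one omitting 5%: 0.0864 SD.

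| Reading SD (mg/dl) | Spurious difference (mg/dl) | Share of 18 mg/dl | False non-inferiority at the margin, bias toward U300 | Power, bias against U300 |
|---|---|---|---|---|
| none omitted | 0 | 0% | 5% | 80% |
| 40 | 3.5 | 19% | 12% | 65% |
| 50 | 4.3 | 24% | 15% | 60% |
| 60 | 5.2 | 29% | 18% | 55% |

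For a bias b, the last two columns are Φ(−1.645 + b/7.2) and Φ((18 − b)/7.2 − 1.645). For b = 4.3 these are Φ(−1.05) = 15% and Φ(0.26) = 60%.

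**Direction.** The table assumes omitted highs, and nothing in the documents says that this would differ by arm. The one arm-specific expectation in the protocol concerns lows. If U300 patients left out more lows, their logged mean would rise. That would count against U300 on BG and in its favor on hypoglycemia.

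**Hypoglycemia.** Section X.a expects about 20% of outpatients to have at least one episode. Take a true 20% in both arms.

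- 30% of affected U300 patients unrecorded: 0.20 × 0.70 = 14%.
- 10% of affected U100 patients unrecorded: 0.20 × 0.90 = 18%.
- The apparent difference is 4 percentage points where none exists.

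If instead U100 is fully recorded and 90%, 80%, 70% or 50% of affected U300 patients are recorded, a two-sided 0.05 test with 78 per arm shows a false U300 benefit about 5%, 9%, 17% or 42% of the time, against 2.5% expected in that direction.

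**The case against.** The strongest reply is that the logbook stands in a list of training topics. Neither V.e nor V.g.2 says that the endpoint is computed from it, and silence about the meter does not show that staff would not read it at the visits. This stands: a reader might infer that the logbook is the declared analysis source, and the documents do not say so. They name no source at all, which for a primary endpoint leaves each site to choose.

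Second, hypoglycemia is marked at six contacts after discharge, so capture is not left to the logbook alone. This also stands, and it makes the heavier omission rates less likely. It is still patient report, and fasting BG at two visits cannot supply a daily mean.

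Third, a reader might infer that no analysis could detect the distortion. That goes too far. HbA1c does not depend on the logbook, and an arm difference in logged BG that HbA1c does not share would be a warning. It is no check on hypoglycemia, and it shows a discrepancy without restoring the missing readings.

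Fourth, a reader might infer that the bias favors U300. As shown above, the direction depends on which readings are left out, and the documents do not settle it.

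Finally, a download does not help if a patient chooses not to test. That is correct and limits what the fix can claim.

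**Conclusion.** The point holds as an avoidable exposure to bias, not as a demonstrated bias. It rests on four things in the text: open-label treatment, endpoints that need home readings, a patient-kept logbook as the only named record, and no stated source or check in V.e. Under the assumed omission rates, the spurious BG difference is 3.5 to 5.2 mg/dl. That is below the margin, but enough to raise the one-sided error at the margin from 5% to between 12% and 18%, or to cut power from 80% to between 65% and 55%. The hypoglycemia illustration gives 14% versus 18% with no true difference. All of these depend on assumed omission rates that differ by arm; with equal rates the BG bias vanishes. HbA1c offers partial protection for mean glycemia and none for hypoglycemia. A change is worth making because it is cheap and protects a primary endpoint.

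**What to change.** In V.d and V.e, state that meter memory is downloaded or read at the existing 1- and 3-month visits. Make it the primary source for mean daily BG and for events below 70 and below 40 mg/dl. Use the logbook or patient report only where no meter record exists. Report by arm the share of patients on the fallback source and the number of readings per patient; the second shows whether testing itself differed. Set the BG result beside the HbA1c result and comment on any disagreement.

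The cost is a few minutes at two visits already planned, with no change to the sample size. Patients need meters with readable memory; the plan does not say that the trial supplies them, so this has to be settled. Some patients will forget the meter, so the fallback stays. Selective testing remains: a stated schedule of home readings and a minimum-readings rule for the endpoint would reduce it but not remove it.

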Withdrawal criteria	x	x	x	x	x	x	x	x	x	x
Dose adjustment		x	x	x	x	x	x	x	x	x
Efficacy										
Vital signs ¹	x									x
Phys Exam ¹	x									x
Body weight	x									x
BMI	x									x
HbA1c	x									
Fasting BG	x	x	x	x	x	x	x	x	x	x
Pre-meal BG	x	x	x	x	x	x	x	x	x	x
Safety										

Adv events	x	x	x	x	x	x	x	x	x	x
Hypoglycemia	x	x	x	x	x	x	x	x	x	x
Urine pregnancy test	x									x
Trial material										
Drug dispense ²	x									

¹At time of study enrollment and hospital discharge ²As needed

Flow Chart: Aim 2, Outpatient Study

Visit Type	Hospital Day 1	TC	Clinic visit	TC	TC	TC	Clinic visit
Visit #	1	2	3	4	5	6	7
Time-wks	0	2	4	6	8	10	12
Inf. consent	x						
Incl/excl criteria	x						
Randomization	x						
Withdrawal criteria		x	x	x	x	x	x
Drug Compliance		x	x	x	x	x	x
Dose adjustment		x	x	x	x	x	x
Efficacy							
Vital signs	x		x				x
Phys Exam	x		x				x
Body wgt	x		x				x
BMI	x		x				x
HbA1c	x		x				x
Fasting BG	x		x				x
Safety							
Adv events	x	x	x	x	x	x	x
Hypoglycemia	x	x	x	x	x	x	x
Urine pregnancy test	x		x				
CMP or BMP	x		x				x
Trial material							
Drug dispense	x		x				
Drug account	x		x				x

IX. Potential Risks to the Subject:

IX.a. Hypoglycemia. It is possible that following the proposed protocol, patients receiving insulin glargine U300 and U100 may develop hypoglycemia. The risk of hypoglycemia in non-ICU patients treated with subcutaneous insulin is between 5–30% (12, 17, 41, 42). The number of hypoglycemia will be analyzed statistically. For the purpose of this analysis, hypoglycemia is defined as a BG < 70 mg/dL. Severe hypoglycemia is defined as BG < 40 mg/dL.

X. Protection against risks:

We will follow safeguards to minimize the risk to our subjects: a) we will carefully monitor capillary BG at the bedside using a hand-held glucose meter, b) only experienced nurses/or phlebotomist will draw blood samples, and c) women of reproductive age who are sexually active will undergo a urine pregnancy tests prior to participation in the study. To prevent significant clinical events, no patients with history of significant liver, renal impairment or cardiac failure will be recruited in this study.

X.a. Hypoglycemia: We expect that approximately 10% in the inpatient setting and ~20% in the outpatient (post-discharge) arm will experience one or more episodes of hypoglycemia. To minimize the risk of hypoglycemia, the starting dose will be reduced in the basal bolus insulin regimen (TDD: 0.3 units

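### Aim 2 defines hypoglycemia by glucose value alone, so an assisted post-discharge episode with no value below 70 mg/dl is absent from the hypoglycemia rate (minor; cheap to improve)

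*Combined protocol and SAP*

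**What the plan says.** All references are to the combined protocol and SAP.

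- **Data collected.** V.e item 1c lists, for follow-up after discharge, "Hypoglycemic events (BG < 70 mg/dl and < 40 mg/dl".
- **Analysis definition.** IX.a states: "For the purpose of this analysis, hypoglycemia is defined as a BG < 70 mg/dL". It continues: "Severe hypoglycemia is defined as BG < 40 mg/dL". These match the inpatient definitions in IV.c items 6 and 7.
- **Outcome.** V.g.2 begins its list for Aim 2 with "Secondary outcomes include rate of hypoglycemia during follow-up" and gives no other definition. The same list separately includes "complications and emergency room visits or hospital readmissions at 12 weeks post-discharge".
- **Hypothesis.** Section B (Specific Aims, Aim 2) expects fewer hypoglycemic events with U300 than with U100.
- **Places that leave room for an episode without a reading.** V.c item 5 trains patients in "Hypoglycemia prevention, recognition and management". The V.f dosing table makes an increase conditional on "no hypoglycemia or no random BG (RBG) <70 mg/dL", which names hypoglycemia beside the glucose threshold. The table headed "Flow Chart: Aim 2, Outpatient Study" marks Hypoglycemia at every post-discharge contact. None of these says how an episode without a reading would enter the outcome.

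**The concern.** In hospital, staff check capillary glucose at the bedside (section X). After discharge, the trial depends largely on the patient's own meter and logbook (V.c items 3 and 4). A patient who is confused or being helped by someone else may take no reading, or may take the first one after treatment, when the value has already recovered to 70 mg/dl or more. Under the written definition that episode is not hypoglycemia. A second, smaller consequence is that severity is read from the meter alone: an episode at 40-69 mg/dl that needed another person's help is counted exactly like one that the patient corrected unaided.

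At stake is how completely one secondary outcome describes safety. Less hypoglycemia with U300 is a stated Aim 2 hypothesis, and V.a presents U300 as the expected safer option. The episodes that the rule can omit include clinically important ones. The hypoglycemia table could show none of them while an emergency-visit or adverse-event table shows one.

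**Working it through.** **1. The plan's own sample-size figure, and whether it depends on this definition.** V.g.1 carries over the Aim 1 inputs: margin 18 mg/dl, SD 45 mg/dl, true difference 0, one-sided test, 80% power. The alpha is not stated; 0.05 is assumed.

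n per group = 2 × (1.645 + 0.842)² × (45/18)² = 2 × 6.185 × 6.25 = 77.3, rounded up to 78.

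This reproduces the stated 78. The inputs concern mean daily glucose only, so the hypoglycemia definition affects neither the 78 nor the 90 recruited per group.

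**2. Types of post-discharge episode set against the definition.**

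| Episode | In the BG <70 count? | In the BG <40 count? | Other possible record |
|---|---|---|---|
| Value 40-69, self-treated | Yes | No | Adverse event |
| Value 40-69, another person's help needed | Yes, same as the row above | No | Emergency visit, readmission, adverse event or SAE |
| Value below 40 | Yes | Yes | Same |
| Help needed; value below 70 taken by ambulance or emergency staff and obtained by the site | Yes, because the definition does not restrict the source | Only if below 40 | Same |
| Help needed; no value taken or retrieved, or first value after treatment already 70 or more | **No** | **No** | Same, if reported |

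The last row is the gap. The second row is the loss of clinical severity. No text in V.e, V.g.2, IX.a or XVI carries an episode from the other records into the hypoglycemia rate when there is no qualifying value.

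**3. Weight of one patient in the overall rate.** The patient must have no other value below 70 during follow-up, otherwise the incidence does not change. X.a expects about 20% of outpatients to have at least one episode; 20% is used in both arms. The 45 is an assumed half enrolment, since Aim 2 takes only patients with HbA1c of at least 7.5%.

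Half-width of the 95% CI for the difference = 1.96 × √(2 × 0.2 × 0.8 / n).

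| n per arm | One patient (100/n, points) | Half-width (points) | Ratio |
|---|---|---|---|
| 90 | 1.1 | 11.7 | 0.095 |
| 78 | 1.3 | 12.6 | 0.102 |
| 45 (assumed) | 2.2 | 16.5 | 0.134 |

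**4. Weight of one patient in a sparse category.** Exact (Clopper-Pearson) two-sided 95% upper limits, for assumed counts:

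| Count | n=90 | n=45 (assumed) |
|---|---|---|
| 0 | 4.0% | 7.9% |
| 1 | 6.0% | 11.8% |
| 2 | 7.8% | 15.1% |

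These limits would apply to any rare event in arms of this size. They show only that one patient is more visible among serious episodes than in the overall rate.

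**5. Contacts at which a question could be asked.** The Aim 2 flow chart marks Hypoglycemia at weeks 2, 4, 6, 8, 10 and 12, which makes six contacts after discharge.

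**The case against.** The strongest reply is that a glucose threshold is a sound choice here. The trial is open label, the thresholds are objective and the same in both arms, and they match the inpatient definitions. A report of needing help depends on people who know the assignment. This stands, and is the reason to leave the glucose counts alone and report anything clinical beside them.

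The second reply is that serious episodes are recorded elsewhere. V.e item 3 collects readmissions and emergency visits, and V.g.2 analyses them. Adverse events are marked at all six post-discharge contacts. The SAE definition in XVI covers hospitalization and medically important events, and the DSMB meets every six months. This also stands in large part: a reader might infer that these episodes are lost to the trial, and the documents do not support that. What remains is that nothing connects those records to the hypoglycemia outcome, and an episode treated at home by a relative need not produce an emergency visit or admission.

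The third reply is that the gap needs several conditions together and that V.g.2 names no clinically severe outcome for Aim 2, so the proposal is partly a request for a new category. That is fair, and it limits the weight of the point.

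A reader might also take the absence of Fasting BG marks at the telephone contacts in the flow chart as a sign that glucose is not reviewed there. That inference fails. Dose adjustment is marked at each call, V.d provides dosing advice after each call, the V.f table needs fasting values over three consecutive days, and V.e item 1a collects fasting and premeal glucose. The calls rely on home readings.

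**Conclusion.** The point holds as a minor one. By its stated rule, and not merely through missing detail, the plan excludes from the Aim 2 hypoglycemia rate an assisted or consciousness-altering episode with no value below 70 mg/dl from any source, and it does not separate an assisted episode at 40-69 mg/dl from a mild one.

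The number of such episodes cannot be derived from the documents, and every event count used above is assumed. On the overall rate, one patient is worth about a tenth of the confidence half-width at n=90 and would rarely change the comparison.

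A reader might go further and conclude that the omission favors one arm or invalidates the hypoglycemia analysis. Nothing in the documents supports either: the rule is identical in both arms, and nothing indicates that unmetered episodes would be commoner in one. Nor should it be read as excluding ambulance or emergency values, since any source of a value below 70 qualifies. The primary endpoint of mean daily glucose is unaffected.

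**What to change.** Keep the BG <70 and <40 definitions as they are. Add one category to V.e item 1c and V.g.2, reported by arm: *clinically severe post-discharge hypoglycemia (altered consciousness, need for another person's help, or an emergency visit or admission for hypoglycemia), whether or not a glucose reading exists.*

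Ask about it at the six scheduled contacts, and check the answers against the emergency-visit, readmission and adverse-event records already collected. Any value below 70 found there already qualifies for the glucose counts and should be entered. A second version of the overall hypoglycemia rate is not needed. Inpatient definitions and dosing rules do not change.

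The cost is one definition sentence, one question at contacts that already carry a Hypoglycemia mark, a check against existing records and one extra table row. The downside is some judgement in an open-label setting, which is why the category sits beside the glucose-only counts and is not merged into them.

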- Glulisine insulin will be given in three equally divided doses before each meal. To prevent hypoglycemia, if a subject is not able to eat, glulisine insulin dose will be held.

* If patient was on basal only therapy consider adding prandial dose as calculated above.

Insulin Naïve Patients Treated with Oral Agents or GLP1-RAs Prior to Admission

- Discontinue oral antidiabetic drugs on admission.
- Starting total daily insulin dose:
 - 0.4 U/Kg/day when randomization BG between 140-200 mg/dL
 - 0.5 U/Kg/day when randomization BG between 201-400 mg/dL
 - Reduce TDD to 0.3 units per kg in patients ≥ 70 years of age and/or with an eGFR < 60 ml/min.
- Half of TDD will be given as glargine U300 or U100 and half as glulisine.
- Glargine will be given once daily, at the same time of the day.
- Patients will receive the full-dose of glargine insulin (even if NPO) the day of surgery or diagnostic procedure(s).
- Glulisine insulin will be given in three equally divided doses before meals. To prevent hypoglycemia, if a subject is not able to eat, the dose of glulisine will be held.

Supplemental insulin. Glulisine insulin will be administered following the “supplemental/correction insulin scale” protocol (Appendix 1).

- If a patient is able and expected to eat most of his/her meals, supplemental insulin will be administered before meals and at bedtime following the “usual” dose of the insulin scale protocol.
- If a patient is not able to eat, supplemental insulin will be administered every 6 hours following the “sensitive” dose of the supplemental insulin scale protocol.

Basal Insulin adjustment.

- Daily basal (glargine U300 and U100) insulin dose will be adjusted as follow:

- If the fasting and pre-dinner BG is between 100 - 140 mg/dl in the absence of hypoglycemia the previous day: no change
- If the fasting and pre-dinner BG is between 141 - 180 mg/dl in the absence of hypoglycemia: increase basal insulin by 10% every day
- If the fasting and pre-dinner BG is 181- 299 mg/dl in the absence of hypoglycemia the previous day: increase basal insulin (glargine) dose by 20% every day
- If the fasting and/or pre-dinner BG is ≥ 300 mg/dl in the absence of hypoglycemia the previous day: increase basal insulin (glargine) dose by 30% every day
- If the fasting and pre-dinner BG is between 70 - 99 mg/dl in the absence of hypoglycemia: decrease TDD (basal and prandial) insulin dose by 10% every day

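### V.f ties its single-reading low-glucose rows to a two-weekly cycle, and the visible text of V.c, V.d and V.f prints no route for acting on a home low sooner

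*Combined protocol and SAP*

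**What the plan says.** **Trigger.** The V.f table acts on single readings at the low end. One row begins "If any FBG or RBG 40- 69 mg/dl" and requires a cut of 8 IU or 20% of the total daily dose. The next begins "If any FBG or RBG < 40 mg/dl" and requires a cut of 30-40%.

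**Timing.** The table is introduced by "Primary care physicians will be provided with the following algorithm for outpatient basal insulin dose adjustment every 2 weeks". V.d adds: "A member of the diabetes research team will contact patients via telephone call every 2 weeks for a total of 3 months". It also says when dose advice is given: "Recommendation on insulin adjustment to be provided after each telephone contact and/or clinic visit by a licensed physician (fellow or study physician". Clinic visits are at 1 and 3 months. In the chart titled "Flow Chart: Aim 2, Outpatient Study", the dose-adjustment row is marked at weeks 2, 4, 6, 8, 10 and 12 and nowhere else.

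**What patients are told.** V.c lists training in "Hypoglycemia prevention, recognition and management", along with meter use and a logbook. None of V.c, V.d or V.f states a glucose value at which the patient should call before the next contact.

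**Inpatient counterpart.** Section IV.f (Basal Insulin adjustment) has cuts of the same percentage, 20% below 70 mg/dl and 30-40% below 40 mg/dl, but within a daily cycle: "Daily basal (glargine U300 and U100) insulin dose will be adjusted as follow". The Aim 1 flow chart marks dose adjustment on each of Days 2 to 10.

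**The concern.** The trigger and the timing do not fit together. A reading below 40 mg/dl is, by the protocol's own rule, reason to take 30-40% off the dose. Yet the only printed occasion for doing so is the next two-weekly contact. If a site runs the outpatient phase on scheduled contacts alone, a patient with a recorded low may keep taking the same once-daily glargine dose until the next call. The same contacts are also where V.f raises the dose by 2 or 4 IU, so a low that follows an increase has no scheduled correction until the next cycle.

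Hypoglycemia is the main risk that the protocol names (Section IX.a). Several features of V.b and the concomitant-medication rules lower it: many patients leave on 50% or 80% of the hospital dose, and sulfonylurea is halved or stopped. However, some basal-bolus patients leave on 100% of the hospital dose. What is at stake is patient safety. The schedule is the same in both arms, so bias, power and analysis are not in question.

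**Working it through.** **1. Reproduce the plan's interval.** Contact weeks in the Aim 2 flow chart are 0, 2, 4, 6, 8, 10 and 12. Each gap is 2 weeks x 7 = 14 days, so there are six gaps of 14 days. This agrees with V.d and V.f. Week 0 is taken here as the start of outpatient dosing.

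**2. Wait from a home low to the next scheduled adjustment.** Let the low occur at time T within a 14-day gap; the wait is 14 - T.

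- Maximum: 14 days.
- Mean, if T is uniform (assumption): 14 / 2 = 7 days.
- Share waiting more than 1 day: 13 / 14 = 93%.
- Share waiting more than 7 days: 7 / 14 = 50%.

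These figures assume no unscheduled contact.

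**3. Compare with the inpatient rule.** Dose adjustment is marked daily on Days 2 to 10, an interval of 1 day against 14. Bedside monitoring makes a shorter cycle natural, so the contrast shows only how the timing differs for cuts of the same percentage.

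**4. How many patients could have a low at all.** Section X.a forecasts about 20% of outpatients with at least one episode. The prior discharge study, which used different HbA1c cut-offs, gave about 30% on oral agents plus basal insulin. For basal-bolus it gave close to 40% (V.a) or over 40% (Section II). Only Aim 1 patients with HbA1c of 7.5% or more are invited to Aim 2, and the protocol gives no expected share. Entry of 50%, 75% and 100% of the 180 is therefore an assumed range.

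| Aim 2 entrants (assumed) | at 20% | at 30% | at 40% |
|---|---|---|---|
| 90 | 18 | 27 | 36 |
| 135 | 27 | 40.5 (about 41) | 54 |
| 180 | 36 | 54 | 72 |

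At each rate, these are upper bounds on the patients affected by delay. They count anyone with any reading below 70 mg/dl, and some of those patients would call unprompted.

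**5. What cannot be computed.** The documents give no outpatient rate for readings below 40 mg/dl and no rate of recurrence while the dose is unchanged. Harm from waiting is therefore not estimated.

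**The case against.** The strongest reply is that this argues from silence about patient-facing instructions. A line telling patients when to call would naturally sit in the consent form, contact page, discharge sheet or logbook. Consent and contact pages are not in the published text, and the content of the V.c training is not printed. This stands: the instruction cannot be shown to be absent from the trial, only from the visible V.c, V.d and V.f.

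The visible text also leaves room for earlier action. V.d speaks of each telephone contact without restricting it to scheduled ones, and primary care physicians hold the algorithm too. A two-weekly look-back asking whether any reading was low is coherent, since it blocks up-titration and forces a cut. This stands as well. What remains is that the algorithm is labelled two-weekly, and the visible sections do not say when a patient should report a low to anyone.

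Section X.a says the total daily dose is cut by 20% following every episode below 70 mg/dl. If that covers outpatients, the plan already intends an event-driven cut and only the timing and reporting route are unprinted. Its neighbouring sentences (admission dose, intravenous dextrose) are inpatient measures, so the scope is ambiguous. The point does not rest on either reading.

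A reader might go further and infer that the protocol requires patients to wait 14 days after a severe low, or that 18 to 72 patients would be harmed. The documents support neither. No text forbids an earlier change, and the counts cover any low, not any injury.

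**Conclusion.** The point holds as a modest patient-safety improvement. V.f attaches cuts triggered by one reading to a two-weekly cycle, and the visible outpatient sections do not release those cuts from it. On scheduled contacts alone the delay is up to 14 days; the 7-day mean rests on an even spread of lows between contacts. Confidence is medium, because training material or unpublished pages may already carry a call instruction.

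**What to change.** 1. In V.d and V.f, state that the 40-69 and <40 mg/dl rows are applied by the study physician at the time a low is reported, are not held to the two-week cycle, and are notified to the primary care physician.
2. In V.c and V.d, instruct patients to call the study team the same day for any reading below 40 mg/dl or any symptomatic low. Extending this to any reading below 70 mg/dl is preferable, but is more open to debate.
3. Keep the two-weekly cycle for up-titration and for the 70-99 mg/dl row. No dose step changes in size.
4. Log these calls in the same way in both arms.
5. If the training material already contains such an instruction, a cross-reference in V.d is enough.

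**Cost.** A short amendment, a line in the logbook, and some unscheduled calls to the team that already makes the two-weekly ones. With the wider threshold (below 70 mg/dl) and the 20% forecast, about 20 per 100 Aim 2 patients would call at least once over three months: 18 if 90 enter, 36 if 180 do. The downside is slightly more self-reported lows, prompted equally in both arms.
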